12. REFERENCES	16
APPENDICES.....	18
APPENDIX A: PARTICIPANT ELIGIBILITY CHECKLIST.....	19

PROTOCOL SYNOPSIS

TITLE	A Randomized Controlled Trial Comparing Apixaban Versus Enoxaparin Following Microsurgical Breast Reconstruction
STUDY PHASE	Interventional
INDICATION	Unilateral or bilateral microsurgical breast reconstruction with free abdominal flaps (i.e. muscle-sparing transverse rectus abdominis musculocutaneous [TRAM] and/or deep inferior epigastric artery perforator [DIEP]) flap) and who are found to have a Caprini score of ≥ 7
INVESTIGATIONAL PRODUCT OR PROCEDURE	Apixaban, Enoxaparin
PRIMARY OBJECTIVE(S)	To examine the rate of bleeding events in patients receiving oral apixaban versus subcutaneous enoxaparin
SECONDARY OBJECTIVE(S)	To examine the rate of VTE events in patients receiving oral apixaban versus subcutaneous enoxaparin
TREATMENT SUMMARY	Eligible patients will be randomized to one of the following 2 treatment groups: 1) Apixaban 2.5 mg PO BID starting 12 hours after completing skin closure. 2) Enoxaparin 40 mg SC QD starting 12 hours after completing skin closure.
SAMPLE SIZE	100

[figure not shown]
SCHEMA

Figure 2. Clinical Protocol

LIST OF ABBREVIATIONS AND DEFINITION OF TERMS

AE	Adverse event
BID	Twice daily
CRF	Case report/Record form
CTCAE	Common Terminology Criteria for Adverse Events
DIEP	Deep inferior epigastric artery perforator
DLT	Dose Limiting Toxicity
DSMB	Data Safety Monitoring Board
DVT	Deep Vein Thrombosis
HIV	Human Immunodeficiency Virus
HTN	Hypertension
IRB	Institutional Review Board
IV	Intravenous
PACU	Post-anesthesia care unit
PE	Pulmonary Embolism
PO	By mouth
REDCap	Research Electronic Data Capture
SAE	Serious adverse event
SC	Subcutaneous
TRAM	Transverse rectus abdominis musculocutaneous
ULN	Upper limit of normal
UNK	Unknown
VTE	Venous thromboembolism
WHO	World Health Organization

1. OBJECTIVES

1.1. Primary Objective

To examine the rate of bleeding events in patients receiving oral apixaban versus subcutaneous enoxaparin.

1.2. Secondary Objectives

To examine the rate of VTE events in patients receiving oral apixaban versus subcutaneous enoxaparin.

2. BACKGROUND

2.1 Study Disease

Venous thromboembolism (VTE) is a common complication in patients undergoing surgery that can have devastating consequences (1-3). While symptomatic deep venous thrombosis (DVT) can lead to severe post-thrombotic syndrome in 10% of patients, symptomatic pulmonary embolism (PE) is the most common cause of preventable in-hospital death with a mortality rate of 10% within the hour and 17% at three months (4). The importance of prevention has been recognized and validated instruments, such as the Caprini Risk Assessment Model, have been introduced. These aid in clinical decision-making regarding chemoprophylaxis. The occurrence of 'breakthrough' VTE events, defined as the occurrence of VTE events despite guideline-compliant chemoprophylaxis, however, highlights the need for changes in clinical practice to improve clinical outcomes.

2.2 Study Agent/Device/Procedure

Review of enoxaparin mechanism and pharmacodynamics

Enoxaparin is a low molecular weight heparin commonly provided as chemical VTE prophylaxis in surgical patients. Enoxaparin accelerates the activity of antithrombin, which, in turn, accelerates the rate at which Factor Xa is inactivated. Factor Xa inactivation results in decreased conversion of prothrombin to thrombin. Inhibition of this critical step in the coagulation cascade decreases the likelihood that clot will form. Enoxaparin's peak response occurs at three to five hours after subcutaneous injection, with a half-life of seven hours. Enoxaparin metabolism occurs by metabolism in the liver and excretion via the kidneys. Patients with creatinine clearance of less than 30 mL/min demonstrate 30% decreased enoxaparin clearance. Enoxaparin exhibits linear pharmacokinetics and an inverse relationship between renal impairment and drug activity.

Review of apixaban mechanism and pharmacodynamics

Apixaban was introduced in 2014 and is a highly selective inhibitor of free and prothrombinase-bound FXa. It has a half-life of 8 to 15 hours and multiple pathways of elimination, including renal and fecal excretion with minimal drug-drug interactions. The recommended dose for VTE prophylaxis is 2.5mg PO BID. The superiority of apixaban over enoxaparin has been demonstrated in landmark trials of hip and knee replacement, where lower rates of VTE were seen without increased bleeding.

For clinicaltrials.gov compliance

Use of apixaban for VTE chemoprophylaxis following autologous breast reconstruction has not been approved by the FDA.

2.3 Rationale

Venous thromboembolism (VTE) continues to be a major patient safety issue after surgical intervention. Significant morbidity and mortality are associated with the development of VTE. With over 100,000 annual VTE-related deaths in the U.S., this disease entity represents the most common cause of preventable in-hospital death (10, 11). Furthermore, the associated economic burden is substantial, with annual costs to the U.S. healthcare system in excess of \$7 billion (12).

The importance of VTE prevention has been recognized by organized plastic surgery. Significant resources have been

invested into raising awareness and improving VTE risk stratification and prophylaxis in patients undergoing plastic and reconstructive surgery. Initiatives such as the American Society of Plastic Surgeons (ASPS) VTE Task Force, the Plastic Surgery Foundation (PSF)-funded VTE Prevention Study (VTEPS) as well as initiatives by the American Association of Plastic Surgeons (AAPS) reflect the significant emphasis placed on this particular area of clinical research (3, 11, 13, 14). Important questions, however, remain unanswered and include issues such as appropriate dosing as well as duration of VTE chemoprophylaxis. Furthermore, mechanisms underlying 'breakthrough' VTE events, defined as VTE events despite guideline-compliant chemoprophylaxis, remain unknown. VTEPS demonstrated that despite daily enoxaparin prophylaxis 1 patient in 25 with a Caprini score >8 had a breakthrough VTE event (3). The occurrence of breakthrough VTE events highlights the need for an improved approach to VTE chemoprophylaxis.

VTE risk stratification and clinical research in other specialties have identified cancer patients as a particularly vulnerable patient population (15, 16). Of these, breast cancer patients represent the largest group treated by plastic surgeons. Symptomatic VTE has been reported in up to 4% of patients undergoing autologous reconstruction using abdominal flaps (17). An up to 20% rate of asymptomatic VTE after autologous reconstruction has been reported (18). In light of rising numbers of breast reconstruction in the U.S., with more than 18,000 autologous reconstructions in 2013, a 35% increase in the number of annual breast reconstructions since 2000, and over 106,000 breast reconstructions in 2015 alone, the number of patients at risk for VTE is alarmingly high (19-21). It is important to note that an increased rate of DVT formation has been reported following autologous vs. implant-based breast reconstruction despite guideline-compliant prophylaxis (22). These findings are particularly relevant in light of an increasing number of patients undergoing prophylactic bilateral mastectomy with immediate reconstruction. As such, it is of no surprise that the ASPS VTE Task Force identified "major breast reconstruction" as a procedure warranting additional prophylactic considerations (11). Given the large number of patients at risk, particular emphasis on understanding the processes leading to VTE development in this patient population is warranted. A recent retrospective study in over 1500 patients who underwent body contouring procedures (LMWH [N=454]; rivaroxaban [N=703], apixaban [N=415]) demonstrated similar rates of bleeding-related adverse events (37).

2.4 Study Design

For clinicaltrials.gov and Stanford Clinical Trials Directory compliance

- **Prevention:** protocol designed to assess one or more interventions aimed at preventing the development of a specific disease or health condition
- **Parallel:** one of two groups in parallel for duration of study.
 - 2 intervention arms.
 - **Open:** no masking is used
 - Study is randomized.
 - Safety/Efficacy; Pharmacokinetics.

3. PARTICIPANT SELECTION AND ENROLLMENT PROCEDURES

Refer to the Participant Eligibility Checklist in Appendix A.

3.1 Inclusion Criteria

3.1.1 Adult (>18 years) women who are scheduled to undergo unilateral or bilateral microsurgical breast reconstruction with free abdominal flaps (i.e. muscle-sparing transverse rectus abdominis

musculocutaneous [TRAM] and/or deep inferior epigastric artery perforator [DIEP]) flap) and who are found to have a Caprini score of ≥ 6

3.1.2 Ability to understand and the willingness to sign a written informed consent document.

3.2 Exclusion Criteria

3.2.1 NSAIDs or other anticoagulant intake within 7 days of surgery

3.2.2 Use of other Investigational Agents is prohibited.

3.2.3 Active bleeding, history of bleeding disorder, coagulopathy, heparin-induced thrombocytopenia, liver disease, renal disease (creatinine clearance ≤ 30 mL/min; serum creatinine >1.6 mg/dL), major neurosurgical intervention (brain/spine) within the past 90 days, ophthalmologic procedure within the past 90 days, uncontrolled hypertension, history of alcohol and/or substance abuse prior to 6 months of enrollment, or need for therapeutic anticoagulation

3.2.4 Contraindication to the use of apixaban or enoxaparin

3.2.5 Pregnant or nursing patients will be excluded from the study.

3.3 Informed Consent Process

All participants must be provided a consent form describing the study with sufficient information for participants to make an informed decision regarding their participation. Participants must sign the IRB approved informed consent prior to participation in any study specific procedure. The participant must receive a copy of the signed and dated consent document. The original signed copy of the consent document must be retained in the medical record or research file.

3.4 Randomization Procedures

Attending surgeon and assistant surgeons will be blinded to the randomization status during surgical procedure. Randomization will be determined using a pre-specified randomization list. Once surgery is complete, the study coordinator will notify the surgeon of the randomization ARM the patient is assigned to upon their arrival in post-anesthesia care unit (PACU).

3.5 Study Timeline

Primary Completion:

The study will reach primary completion 18 months from the time the study opens to accrual.

Study Completion:

The study will reach study completion 24 months from the time the study opens to accrual.

4. TREATMENT PLAN

Adult (>18 years) women who are scheduled to undergo unilateral or bilateral microsurgical breast reconstruction with free abdominal flaps (i.e. muscle-sparing transverse rectus abdominis musculocutaneous [TRAM] and/or deep inferior epigastric artery perforator [DIEP]) flap) and who are found to have a Caprini score of ≥ 6 will be approached by the clinical research coordinator during the preoperative clinic visit. Informed consent for randomization and study participation will be obtained.

Exclusion criteria will include contraindication to the use of apixaban or enoxaparin, active bleeding, history of bleeding disorder, coagulopathy, heparin-induced thrombocytopenia, liver disease, renal disease (creatinine clearance

≤ 30 mL/min; serum creatinine >1.6 mg/dL), major neurosurgical intervention (brain/spine) within the past 90 days, ophthalmologic procedure within the past 90 days, uncontrolled hypertension, history of alcohol and/or substance abuse, or need for therapeutic anticoagulation.

Eligible patients will be randomized to one of the following 2 treatment groups (Figure 2):

- 1) Apixaban 2.5 mg PO BID starting 12 hours after completing skin closure.
- 2) Enoxaparin 40 mg SC QD starting 12 hours after completing skin closure.

Patients will be assigned to the respective study groups postoperatively upon arrival in the PACU. Hence, surgeons are blinded at the time of surgery as to study group assignment. Chemoprophylaxis will continue for the duration of the hospitalization. Planned timing of prophylaxis initiation with apixaban and enoxaparin is in alignment with published data from the multicenter VTEPS study, respectively (3, 8, 9, 38). Prophylaxis duration is compliant with guidelines from the American Society of Plastic Surgeons (11). All patients will receive mechanical prophylaxis in the form of sequential compression devices prior to the induction of general anesthesia and continued for the duration of inpatient stay.

The treatment period spans the duration of inpatient hospitalization. While hospitalized, patients will be evaluated daily for symptomatic VTE (DVT and/or PE) and bleeding events. After hospital discharge, patients will be encouraged to report all adverse events (AEs) including, but not limited to, signs/symptoms of DVT/PE and bleeding. Suspected DVT/PE will be evaluated with the appropriate diagnostic assessment, including but not limited to Duplex sonography, chest CT-angiography, or V/Q scan. A mandatory phone interview will take place on Day 90 (± 3 days) to confirm that no 90-day events had been diagnosed or were managed by another institution.

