7. ADVERSE EVENTS AND REPORTING PROCEDURES

7.1 Potential Adverse Events

The primary safety outcome is bleeding during the treatment period or until 2 days after the last dose of the study medication was administered (Lassen et al. NEJM 2020;26:2487-2498). Bleeding is categorized as major, clinically relevant nonmajor, or minor bleeding and as the composite of major and clinically relevant nonmajor bleeding. The definition of major bleeding is acute, clinically overt bleeding accompanied by one or more of the following findings: a decrease in the hemoglobin level of 2 g per deciliter or more over a 24-hour period; transfusion of 2 or more units of packed red cells; bleeding at a critical site (including intracranial, intraspinal, intraocular, pericardial, and retroperitoneal bleeding); bleeding into the operated joint, necessitating reoperation or intervention; intramuscular bleeding with the compartment syndrome; or fatal bleeding. Clinically relevant nonmajor bleeding includes acute, clinically overt episodes such as wound hematoma, bruising or ecchymosis, gastrointestinal bleeding, hemoptysis, hematuria, or epistaxis that does not meet the criteria for major bleeding. Bleeding is categorized as minor if it is clinically overt but is not adjudicated as major or clinically relevant nonmajor bleeding.

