8. STUDY CALENDAR

	Pre-Study	12 -16 hours post surgery ending at time of inpatient discharge	Time of hospital discharge	90 days post surgery
Investigational Agent ^{1,2}		X		
Informed consent	X			
Demographics	X			
Medical history	X			
Concurrent meds	X			
Physical exam	X	X		
Vital signs	X	X		
Height	X			
Weight	X			
Caprini Score	X			
CBC	X	X		
Serum chemistry	X	X		
Adverse event evaluation			X	X
90 Day Phone Call				X

1. Apixaban 2.5 mg PO BID starting 12-16 hours after completing skin closure.
2. Enoxaparin 40 mg SC QD starting 12-16 hours after completing skin closure

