11. STATISTICAL CONSIDERATIONS

11.1 Statistical Design

The primary study outcome is defined as overall bleeding event risk 90 days post-randomization. Secondary patient-oriented outcomes include risk of VTE events. Tertiary outcomes include: length of stay, location of patient on day 90 of follow up (home vs. SNF, etc), and clinically significant wound complications (infection, dehiscence, flap loss).

Process measures to be collected include time to starting anticoagulation after completion of skin closure, number of days patients received anticoagulation treatment, and timing of phone interview follow up.

Conservative estimates from recent retrospective study in over 1500 patients who underwent body contouring procedures (LMWH [N=454]; rivaroxaban [N=703], apixaban [N=415]) are used for our power analysis (37). Using standard formulas, with 80% power to detect a non-inferiority margin of -0.075, and assuming a 1.32% baseline in bleeding events among patients dosed on daily enoxaparin compared with a 1.73% rate of bleeding in direct oral anticoagulant (DOAC) arm patients over 90 days, our analysis expects enrollment size of 37 patients per arm. We conservatively estimate a 25% dropout rate over the course of the study, which results in a sample size of 100 (50 patients per arm).

The primary conclusions of this project will be analyzed based on intention-to-treat where all randomized patients will be analyzed within the groups they were originally allocated to. Two-sided 5% significance levels will be used to identify statistically significant results. Unadjusted analysis of the bleeding risk in apixaban use will be assessed using an exact Pearson chi-squared test. The outcome will be reported as an odds ratio with 95% confidence intervals. Baseline prognostic variables including age, BMI, Caprini score, Elixhauser comorbidity index score, procedure duration, unilateral vs. bilateral will be ascertained upon enrollment and reported by our study group. A subsequent covariate adjusted analysis will be undertaken with an adjusted logistic regression model.

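### Bleeding is counted from assignment on PACU arrival, but both study drugs start at least 12 hours after skin closure, so bleeds before any study drug can count as primary events

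*Combined protocol and SAP*

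**What the plan says.** **Assignment.** Section 4 states "Patients will be assigned to the respective study groups postoperatively upon arrival in the PACU". Section 3.4 adds "Randomization will be determined using a pre-specified randomization list", and section 11.3 repeats that the surgeon learns the arm when the patient reaches the PACU.

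**Outcome clock.** Section 11.1 states "The primary study outcome is defined as overall bleeding event risk 90 days post-randomization". Sections 9, 9.1 and 11.4 say the same. The analysis is by intention to treat.

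**First dose.** Section 4 has "Apixaban 2.5 mg PO BID starting 12 hours after completing skin closure" and "Enoxaparin 40 mg SC QD starting 12 hours after completing skin closure". The calendar in section 8 has "Apixaban 2.5 mg PO BID starting 12-16 hours after completing skin closure" and the same interval for enoxaparin; section 5.1 agrees with the calendar.

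**A second bleeding window.** Section 7.1 defines a primary safety outcome that covers the treatment period or runs to 2 days after the last dose. Section 4 makes the treatment period the whole inpatient stay. The treatment column of the calendar starts 12 to 16 hours after surgery.

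**What counts.** Section 7.1 includes wound hematoma, bruising and ecchymosis. It classes overt bleeding as major if, among other criteria, there is "a decrease in the hemoglobin level of 2 g per deciliter or more over a 24-hour period" or a transfusion of at least 2 units. It names no reference hemoglobin sample and no start time relative to dosing.

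**Related rules.** Section 3.2.3 begins its exclusions with "Active bleeding, history of bleeding disorder, coagulopathy, heparin-induced thrombocytopenia, liver disease". Section 6 withholds or stops drug after major or clinically relevant nonmajor bleeding. Time to starting anticoagulation is collected, but only as a process measure.

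**The concern.** Between PACU arrival and the first dose, neither drug can cause or prevent a bleed. This is also the period just after a long flap operation, and the definitions in section 7.1 capture ordinary surgical events such as a wound hematoma. Such a bleed is a primary event in the assigned arm. Under section 6 the patient may then never receive the drug, yet intention to treat keeps her in the count.

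The plan expects so few bleeds that one or two of these events could decide the comparison. Events common to both arms move the odds ratio, which is the measure to be reported, towards 1. In a trial meant to show that apixaban does not bleed appreciably more, that movement favours an impression of similarity. The trial is open label and the arm is disclosed in the PACU, so early bleeds can also be judged with the arm known.

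**Working it through.** **Inputs from section 11.1:** enoxaparin rate pc = 0.0132; DOAC rate pt = 0.0173; margin 0.075 on the risk difference; 80% power; 37 per arm; 25% dropout; 50 per arm, 100 in total.

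**Input not in the documents:** the pre-dose bleeding risk c, taken as common to both arms. It is an assumption, shown at 1%, 2% and 5%.

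**1. The plan's own figure.** With unpooled variance, n = [pc(1-pc) + pt(1-pt)](z_alpha + z_beta)² / (margin - (pt - pc))².
- Variance sum: 0.01303 + 0.01700 = 0.03003.
- Distance to the margin: 0.075 - 0.0041 = 0.0709.
- At one-sided 5%: 0.03003 × (1.645 + 0.842)² / 0.0709² = 36.9, so 37 per arm.
- Dropout: 37/0.75 = 49.3, so 50 per arm and 100 in total.

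The figure reproduces at one-sided 5%. The stated two-sided 5% level (one-sided 2.5%) would need 47, which is a separate matter.

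**2. Expected events.** 50 × 0.0132 + 50 × 0.0173 = 0.66 + 0.865 = 1.525 in 100 patients.

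**3. Adding pre-dose bleeds.** If the plan's rates apply after dosing, each arm's risk becomes p' = c + (1 - c)p. The pre-dose share of events is 100c / [100c + (1 - c) × 1.525]. Power is Phi((0.075 - d')/SE' - 1.645), where d' is the new risk difference and SE' its standard error at 37 per arm.

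| c | Enoxaparin p' | DOAC p' | Pre-dose share | Odds ratio | Power |
|---|---|---|---|---|---|
| 0 | 1.32% | 1.73% | 0% | 1.32 | 80% |
| 1% | 2.31% | 2.71% | 40% | 1.18 | 62% |
| 2% | 3.29% | 3.70% | 57% | 1.13 | 51% |
| 5% | 6.25% | 6.64% | 78% | 1.07 | 34% |

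Worked line for c = 1%: d' = 0.00406; SE' = sqrt((0.02254 + 0.02639)/37) = 0.0364; 0.07094/0.0364 - 1.645 = 0.31; Phi(0.31) = 0.62. At one-sided 2.5% the power column would read 70%, 50%, 38% and 24%.

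**4. Crossover.** Pre-dose bleeds exceed half of all events when c > (1 - c) × 0.01525, that is c > 0.01525/1.01525 = 1.50%.

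**5. Odds ratio against risk difference.** Take an assumed real excess, 1.32% v 4% after dosing. The odds ratio is 3.11 without pre-dose bleeds and 2.21, 1.85 and 1.45 at c = 1%, 2% and 5%. The risk difference is only multiplied by (1 - c): 2.68 points becomes 2.65, 2.63 and 2.55.

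**6. Does the second window close the gap?** Read with section 4, the treatment period in section 7.1 is the whole hospitalization, and pre-dose bleeds are inside it. Read with the calendar column, it starts at 12 to 16 hours, and they are outside. The text does not settle which reading applies, and neither reading changes the 90-day definition in section 11.1.

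**The case against.** **Counting from randomization is standard intention to treat, and early bleeds balance out.** This is correct in expectation. It means the comparison is not biased between arms by the timing alone. It does not remove the noise, nor the movement of the odds ratio.

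**The margin is on the risk difference, which barely moves.** This stands. A reader might infer that a real excess on apixaban would be hidden. On the margin's scale it is almost fully preserved, and added variance makes non-inferiority harder to claim. The attenuation belongs to the odds ratio, on which no margin is set.

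**The power loss depends on what the plan's rates mean.** This also stands. Section 11.1 gives the DOAC rate over 90 days and does not call either rate post-dose only. If both already include early bleeds, power does not change.

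**Some stronger readings go beyond the text.**
- That early bleeds will outnumber later ones: no pre-dose rate is given, so this is only a possibility.
- That eligibility is fixed before surgery and active bleeding is never rechecked: Appendix A states no timing and the calendar has no eligibility row. What can be said is that no section requires a recheck at assignment. Section 6 does make dosing conditional on the absence of postoperative bleeding.
- That the arm is disclosed 12 or more hours before dosing: PACU arrival follows closure, so under section 4 the interval is shorter than 12 hours.
- That the list slot is fixed before PACU arrival: the documents do not say so.
- That operative blood loss or dilution alone makes a major bleed: section 7.1 also requires acute, clinically overt bleeding.

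**Conclusion.** The gap is real. The outcome clock starts at randomization, assignment is on PACU arrival, both drugs start later, and no section clearly leaves out the bleeds in between. The harm is noise and an odds ratio closer to 1, not a systematic tilt towards either arm.

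The size is conditional. Against about 1.5 expected events, an added pre-dose risk of 1% to 5% would make these bleeds 40% to 78% of the total. The fall in power from 80% to between 62% and 34% further requires that 1.32% and 1.73% be post-dose rates, and it uses a normal approximation with very few events. A reader might infer that the trial cannot answer its question unless this is changed. The documents do not support that, because the pre-dose rate is unknown. The change is worth making because it is inexpensive and removes events that neither drug can have caused.

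**What to change.** **Preferred.** In sections 3.4, 4 and 11.3 (and the matching text in 5.1), release the list assignment as close as practical to the first dose, and confirm the existing 3.2.3 exclusions at that time. The primary outcome then starts at that randomization, and intention to treat is kept.

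**If PACU assignment is kept.** Record the onset time of every bleed. Beside the all-randomized count, pre-specify an analysis of bleeds from a common landmark after skin closure, the same in both arms, among patients event-free at the landmark. List earlier bleeds separately by arm. A fixed landmark is safer than each patient's actual dose time, which could depend on the arm, although a few bleeds before a late first dose would remain.

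**In either case.** Reconcile the bleeding windows in sections 4, 7.1, 8 and 11.1, and the 12-hour and 12-to-16-hour statements. State which existing hemoglobin sample is the reference for the 2 g/dL fall; the calendar shows only one CBC mark across the whole inpatient column. State whether the planning rates include bleeds before the first dose.

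**Cost.** Protocol wording and an onset time on the case report form. The coordinator releases some assignments later, sometimes overnight. A few consented patients who bleed early are not randomized, or are left out of the landmark analysis.
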